Subjects underwent a six-month surveillance protocol biopsy and some received three-month surveillance protocol or indication biopsies per standard of care. For the study, existing biopsy tissue was stained with Sirius Red, providing a measure of fibrosis called (V_{IntFib}) that was quantified by computerized image analysis⁴⁷. Fibrosis is an established measurement of chronic graft injury. ACE, ACE2, Ang II, and Ang-(1-7) protein were measured by radioimmunoassays at the Hypertension and Vascular Research Biomarker Analytic Core at Wake Forest School of Medicine. All data, including protected health information, was stored securely on a HIPAA-compliant REDCap Database hosted by Stanford University School of Medicine. Summary statistics, including frequencies for categorical variables and mean with standard deviation (SD) or median with interquartile range for continuous variables will describe clinical and demographic characteristics. Graphical exploration will assess the data and quantile plots will evaluate the need for log transformation. Measurements below the lower limit of detection of the laboratory will be assigned a value of the lower limit of detection divided by the square root of two. Spearman rank correlation coefficients will be used to assess the correlation between ACE2, ACE, Ang-(1-7), Ang II and the continuous covariates and outcomes. We will estimate sensitivity, specificity, and the area under the receiver operator characteristics curve to assess the clinical predictive value of the biomarkers.

Primary outcome for Aim 1: Early subclinical graft injury.

Cox regression will be used to estimate hazard ratios for the association of biomarker levels with the outcome biopsy-proven graft injury, adjusting for potential confounders. Robust standard errors and clustering by subject ID for patients diagnosed with more than one episode of graft injury during the study period will be used. The time axis will be six months, starting at the time of transplant or time of recovery from the preceding acute injury event, and ending at six months post-transplant. Observations will be right-censored at the time of graft loss, loss to follow up, or withdrawal from the study. The model will be compared to other models that include the time dependent-covariates serum creatinine and eGFR.

Primary outcome for Aim 2: Chronic subclinical graft injury.

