Cox regression will be utilized to estimate hazard ratios for the association of biomarker levels with the outcome biopsy-proven graft fibrosis, adjusting for potential confounders. The time axis will begin at the time of transplant and end at six months post-transplant. Observations will be right-censored at the time of graft loss, loss to follow up, or withdrawal from the study. The model will be compared to other models that include the time dependent-covariates serum creatinine and eGFR.

Missing Data

Subjects may miss lab collections or may be lost to follow up. However the reasons for missing data are presumed to be independent of the values of the predictors ACE, ACE2, Ang II, and Ang-(1-7). Clinical data including covariates and outcomes will be recorded even if a subject is lost to follow up. Therefore missing data will be presumed to be missing completely at random. We chose to handle missing covariate values by multiple imputations due to the longitudinal data and high rate of missing data (23%).

Power

The study was estimated to enroll 30 subjects (final enrollment 29), based on anticipated subjects and estimated incidence of kidney injury (10% in first six months post-transplant). The study was powered to detect a Pearson correlation of 0.56 with a two-sided *p* value of 0.025.

References

- 4. Halawa A. The early diagnosis of acute renal graft dysfunction: A challenge we face. The role of novel biomarkers. Ann Transplant. 2011; **16**(1): 90-8.

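### Aim 1 Cox model: at about 3 injured children, uncorrected clustered robust intervals are too narrow if repeat episodes occur or robust errors cover the whole model, and biomarkers are not imputed

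*Combined protocol and SAP*

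**What the plan says.** Under Approach/Methods, Primary outcome for Aim 1, the analysis is a Cox regression giving "hazard ratios for the association of biomarker levels with the outcome biopsy-proven graft injury, adjusting for potential confounders". The variance rule is "Robust standard errors and clustering by subject ID for patients diagnosed with more than one episode of graft injury". Repeat episodes are provided for, because follow-up time is defined as "starting at the time of transplant or time of recovery from the preceding acute injury event". No jackknife, t reference, penalised likelihood or other few-event method is named. The number of adjusting covariates is not given.

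On biopsy timing, the same section says: "Subjects underwent a six-month surveillance protocol biopsy and some received three-month surveillance protocol or indication biopsies per standard of care".

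The Power section plans 30 subjects, reports 29 enrolled, and cites an "estimated incidence of kidney injury (10% in first six months post-transplant"). Its only power statement concerns a Pearson correlation. No event count, interval property or significance level is given for the Cox model.

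The Missing Data section says: "We chose to handle missing covariate values by multiple imputations due to the longitudinal data and high rate of missing data (23"%). It does not say whether the biomarkers count as covariates for this purpose.

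**The concern.** Clustering by subject gives 29 clusters, which may look adequate. The sandwich variance, however, is driven by the children who contribute events, and the plan's own figures imply about 3. With so few, it tends to understate the variance of the log hazard ratio.

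The variance rule can be read in two ways: robust errors for the whole Aim 1 model, or only when some child has a repeat episode. With repeats, both readings lead to the robust interval. Without repeats, only the first does.

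The hazard ratio for biopsy-proven injury is the Aim 1 result. An interval that is too narrow would exclude a hazard ratio of 1 too often and could make an unrelated urinary ratio look predictive.

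**Working it through.** **The plan's own figure.** The Power section gives r = 0.56, two-sided 0.025 and 30 subjects, but no power level. By Fisher's z, N = ((z for 1 - 0.025/2 + z for power) / atanh(0.56))² + 3. At 85% power this is ((2.241 + 1.036)/0.633)² + 3 = 29.8, so 30. At 80% it is 26.7 and at 90% it is 34.0. The 30 is thus consistent with 85% power for a correlation, and says nothing about the Cox model.

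**Expected injured children.** 0.10 × 30 = 3.0; 0.10 × 29 = 2.9. Under Binomial(29, 0.10), P(0 or 1) = 0.047 + 0.152 = 0.199, P(2) = 0.236 and P(4 or fewer) = 0.84.

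**Coverage without imputation.** Cox fits were simulated for 29 children, conditional on the number injured. The sandwich was built from score residuals summed by subject, with nominal 95% normal intervals. Each scenario had 2,000 runs (simulation error about 0.9 points), or 500 for the tied, time-varying and some repeat scenarios (about 1.7 points).

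| Scenario | Robust, uncorrected | Model-based |
|---|---|---|
| 3 injured, one episode each, HR 1 | 82.0% | 97.2% |
| Same, HR 2 per SD | 81.9% | 97.4% |
| Same, HR 1, two covariates in the model | 85.7% | 98.0% |
| Same, HR 1, injuries tied at months 3 and 6 | 84.6% | 97.0% |
| Same, HR 1, time-varying biomarker | 82.0% | 96.4% |
| 3 injured, repeats present (several settings) | 78.7-82.8% | 88.4-92.6% |
| 2 injured, no repeats, HR 1 | 74.8% | 98.6% |
| 4 injured, no repeats, HR 1 | 88.5% | 96.2% |
| 6 injured, no repeats, HR 1 | 91.3% | 95.2% |

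In the first row the median ratio of robust to model-based standard error is 0.74. Separately programmed runs gave 84.3% with 3 injured and no repeats, 81.8% with 4 episodes in 3 children, 83-85% with biopsy-dated injuries, 75-76% with 2 injured and 89-91% with 6. As a check on the code, 200 subjects with 60 events gave 96.7% for both estimators.

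**Standard cluster correction.** G/(G-1) with G = 29 multiplies the standard error by √(29/28) = 1.018. Coverage in the first row moves only from 82.0% to 82.9%. Adding a t reference on 28 degrees of freedom gives 80-87%.

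**With biomarker imputation.** With 23% of biomarker values missing completely at random and 10 imputations, false positives at nominal 5% with 3 injured were 4-10% without repeats and 7-14% with 4 episodes in 3 children. The 14% comes from a separate run. With an injury indicator in the imputation model they were 8-10% and 10-12%.

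**Jackknife.** With 3 injured, the delete-one-subject jackknife covered 96.0-97.6% in four 500-run scenarios (one tied, two with repeats, one time-varying). Any interval that could not be computed was counted there as covering. In separate runs of about 500, it covered 96.6% without repeats (computable in 493 data sets) and 97.4% with repeats (computable in 500).

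**The case against.** **It may not apply at all.** The robust rule is worded around patients with more than one episode. Read literally, with no repeats, model-based errors are used and there is no inflation. The documents give no repeat rate and no observed injury count. This stands, and it is why the point is conditional. A reader might infer that the Aim 1 intervals are certainly too narrow; the documents do not support that.

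**Imputation may remove it.** The Missing Data section says that laboratory collections may be missed but that clinical covariates and outcomes are recorded even after loss to follow-up. Much of the 23% could therefore be biomarker data. This also stands: without repeats the false-positive range then includes the nominal 5%. With repeats it does not, and the result depends on the imputation model.

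**Biopsy-dated injuries.** A reader might infer that tying injuries to scheduled biopsies makes coverage much worse. Those runs gave 83-85%, within the general range.

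**Three events are uninformative whatever the variance.** Agreed; no correction changes that. It remains a reason not to print an interval that looks more precise than the data allow.

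**A simpler correction exists.** A t reference on injured children minus 1 covered 98-99% with 3 injured. It is conservative: with 2 degrees of freedom the multiplier is 4.303 against 1.960, so the interval is 2.2 times as wide as the uncorrected one, compared with about 1.6 times for the jackknife. It is a defensible alternative. A long chain of contingent methods is not needed.

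**Conclusion.** The point holds conditionally and should be fixed. If repeat episodes occur, or robust errors are used throughout, and biomarkers are not imputed, a nominal 95% uncorrected robust interval covers about 79-86% with 3 injured children, about 75% with 2 and about 89-91% with 6. With 23% of biomarker values imputed, the shortfall shrinks and may vanish without repeats. With robust errors confined to repeat cases and no repeats, model-based coverage is about 97% and the problem does not arise.

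The harm is stated as coverage because the plan sets no significance level for the Cox model. The size rests on assumptions that the documents do not supply: the biomarker distribution, the repeat pattern, the dependence between episodes, recovery time and the number of covariates. Three injured children is a planning figure. Confidence is high in the conditional arithmetic; how likely the conditions are cannot be judged from the documents.

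**What to change.** In the Aim 1 paragraph of Approach/Methods:

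1. State whether robust errors apply to the whole model or only when repeats occur, and report the numbers of injured children and of episodes.
2. Do not base Aim 1 intervals or p-values on the uncorrected robust Wald test. Pre-specify the delete-one-subject jackknife variance, with one named fallback if a refit fails. Firth-penalised Cox with profile-likelihood intervals on first episodes would serve; label it as a different analysis, because it drops repeat episodes. A G/(G-1) factor with 29 clusters is not enough, and going back to model-based errors does not fix the repeat-episode case (about 88-93%).
3. With 0 or 1 injured children, report Aim 1 descriptively.
4. State whether biomarkers are imputed and, if so, pool the jackknife variance by Rubin's rules.

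The cost is wording and a little more analysis, with no new data. Intervals widen (jackknife standard error about 1.6 times the robust one at 3 injured) and tests become slightly conservative. The fallback will sometimes be needed: at 3 injured the jackknife could not be computed in 0-4% of simulated data sets unadjusted, 3-13% with one adjuster and 14-28% with two.

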This was an observational study with a convenience sample of patients recruited from Lucile Packard Children's Hospital's kidney transplant evaluation clinic from 2013 to 2015; 29 subjects completed the study. The recipient ages ranged 1 to 20 years and 34% were living donors. Stanford University School of Medicine IRB approval was obtained (IRB 5136) and informed consent and assent were obtained. Data was collected from information gathered per standard of care. Baseline and post-transplant data included age, sex, self-reported race (Black, White, Hispanic, Asian, or Other), presence of obesity (body mass index ≥95th percentile for age and sex), primary cause of end stage renal disease, dialysis modality, time on dialysis, presence of hypertension, use of ACEi/ARB, presence

of left ventricular hypertrophy, sensitization at transplant, creatinine, estimated glomerular filtration rate (eGFR) by modified Schwartz equation and urine creatinine and protein. Post-transplant data included deceased versus living donor transplant, antigen match, cold ischemia time, immunosuppression including drug levels, and protocol, and indication biopsy results. Specific to the study, plasma and urine protein ACE, ACE2, Ang II, and Ang-(1-7) were collected and analyzed. Data was collected at baseline and post-operatively at 12 hours, 24 hours, daily for 1 week, weekly for 1 month and monthly until 6 months post-transplant. Samples were collected at any clinically significant event concerning for graft injury, including a rise in creatinine, rejection, medication toxicity, and infection.

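### Does censoring at loss to follow-up conflict with recording outcomes after it?

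*Combined protocol and SAP*

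**What the plan says.** All references are to the Combined protocol and SAP, Approach/Methods.

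- **Primary outcome for Aim 1 and Primary outcome for Aim 2.** Each specifies a Cox model running from transplant to six months (for Aim 1, also from recovery after a previous injury). Each carries the same sentence: "Observations will be right-censored at the time of graft loss, loss to follow up, or withdrawal from the study".
- **Missing Data.** It opens with "Subjects may miss lab collections or may be lost to follow up". It presumes that the reasons for missingness do not depend on the four biomarker values, and adds: "Clinical data including covariates and outcomes will be recorded even if a subject is lost to follow up". It concludes: "Therefore missing data will be presumed to be missing completely at random". It puts missing data at 23% and plans multiple imputation for covariates.
- **Opening text of Approach/Methods.** "29 subjects completed the study", and, on the source of the clinical data, "Data was collected from information gathered per standard of care". Subjects had a protocol biopsy at six months, and some had earlier ones. Spearman correlations with the outcomes, and sensitivity, specificity and ROC area, are also planned. None of these has a censoring rule.
- **Power.** Final enrollment is 29, and injury incidence is taken as 10% over six months.

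**The concern.** The Cox sections stop the clock when a subject is lost, while the Missing Data section says outcomes continue to be recorded after that. No sentence links the two, and the plan does not say whether loss means the end of study sampling or the end of chart follow-up. An analyst might therefore code a biopsy-proven injury found after loss either as an event or as censored.

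With few events this could matter. At 10% incidence about 2.9 Aim 1 events are expected, so recoding one event would change 1 / 2.9, about a third, of the expected number. Because the six-month biopsy is the only one every subject has, the outcome of a subject lost mid-study would usually be found after the loss.

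The missing-completely-at-random presumption also draws partly on the sentence about recording outcomes. If the Cox models do not use those outcomes, that support looks weak.

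**Working it through.** **1. The passages side by side.**

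| Question | Cox sections (Aims 1 and 2) | Missing Data |
|---|---|---|
| What is collected after loss? | Not addressed | Clinical covariates and outcomes |
| What enters the Cox model after loss? | Nothing; the observation is censored | Not addressed |

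The two texts answer different questions. Censoring at time *t* means the subject leaves the risk set at *t*, and no later event is counted in that model. Someone programming either model from its own section would censor. Recording more than one model uses is not a contradiction, and the Spearman and ROC analyses, which need a biopsy outcome but have no censoring rule, could use the later outcomes.

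**2. Why the rule is reasonable.** Clinical data come from routine care, so they can continue after a subject stops giving study samples. Biomarker values cannot. If the serial biomarker values enter the model, as the sampling schedule suggests, stopping the clock at the end of sampling avoids carrying a biomarker beyond its last measurement.

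**3. How many records are affected.** Inputs: final enrollment 29 (Power); completers 29 (opening text of Approach/Methods).

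Lost or withdrawn = 29 - 29 = **0**. Records whose coding depends on the question: 0 of 29.

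**4. What if the completer count hides some losses?** Suppose *k* subjects were lost (an assumption; the documents show none) and each carries the full 10% risk after loss. This is an upper bound, because an injury found before loss counts anyway.

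Expected Aim 1 events in total = 0.10 × 29 = 2.9. Expected outcomes in question = 0.10 × *k*. Chance of at least one = 1 - 0.9^*k*.

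| *k* | Outcomes in question | Share of 2.9 | Chance of any |
|---|---|---|---|
| 0 | 0 | 0% | 0% |
| 1 | 0.1 | 3.4% | 10% |
| 2 | 0.2 | 6.9% | 19% |
| 3 | 0.3 | 10.3% | 27% |

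The documents give no fibrosis incidence, so no corresponding Aim 2 figure can be worked out.

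**5. The missing-data rationale.** With 0 subjects lost, none of the 23% comes from loss to follow-up, whatever its denominator (the documents do not state one). It must come from collections missed by subjects who stayed in the study. The Missing Data section already names missed collections as a source and already states the premise that covers them, namely independence from the biomarker values. The sentence about recording outcomes adds nothing for this sample, but removing it would leave the presumption and the imputation as they are. Multiple imputation needs only the weaker missing-at-random condition, given a suitable imputation model, so it does not depend on that sentence.

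**The case for a change.** The strongest reply is that the literal reading leaves something unexplained. If the Cox models drop outcomes after loss, it is odd to cite their recording in support of a missingness presumption. A plan should also define loss to follow-up, since end of sampling and end of chart follow-up give different censoring dates. With about three events expected, even one disputed event would matter, and a few added sentences would cost almost nothing.

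Part of this stands. The term is undefined, and the recording sentence is poor support for the presumption. The rest does not lead to a change. The third-of-events figure requires a lost subject with a later injury, and the documents show no lost subject. A definition would fix a date for nobody, and a sentence saying that later outcomes stay out of the Cox models would only repeat the existing rule. Limiting such outcomes to a descriptive listing could do harm, because it might be read as barring them from the Spearman and ROC analyses, where they may be legitimate.

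**Conclusion.** The concern does not call for a change. The censoring rule is stated for both Cox models and settles what enters them; the Missing Data sentence is about data collection. What remains is an undefined term and a loosely worded rationale, which analysts can handle sensibly by applying the rule as written and reporting how many subjects were lost, withdrew or lost the graft.

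The effect is 0 of 29 records, with no hazard ratio changed. This assumes that final enrollment counts everyone who entered and that completing the study excludes loss and withdrawal. If that is wrong by up to three subjects, at most 0.3 of an expected 2.9 Aim 1 outcomes would be in question, and the stated rule would still decide how to code them. The completer count says nothing about graft loss, but censoring there is a valid cause-specific analysis and is not in dispute.

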Renal Transplant Injury and the Renin-Angiotensin System in Kids (RETASK) [name], PI

Abstract

Kidney disease is a major source of childhood morbidity and mortality. Kidney transplants improve quality of life and life expectancy. Renal graft injury is a significant problem and early identification is critical. No biomarkers exist to identify subclinical injury. Biopsies are the gold standard but are invasive and can miss early injury. The renin-angiotensin system (RAS) is activated in renal injury. The alternative RAS pathway ACE2/Ang-(1-7)/mas is important in counteracting these harmful effects. The components of these pathways are excreted in the urine and are altered in renal injury. The aims of this proposal are to develop noninvasive biomarkers of 1) early and 2) chronic subclinical graft injury. The project was an observational study with a convenience sample of children undergoing renal transplantation. The profile of these pathways in the urine will be compared to outcomes of 1) renal biopsy-confirmed early graft injury and 2) chronic graft injury using Cortical Fractional Interstitial Fibrosis Volume (V_{IntFib}) on biopsy specimens. The components of this pathway are novel potential biomarkers and have not been previously evaluated in this population. The findings of this proposal may enable more prompt diagnosis and more effective treatment of renal graft injury in children.

Specific Aims

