In pediatric kidney transplant patients, rejection, medication toxicity and ischemia cause early and chronic renal allograft injury, which reduces graft lifespan and patient survival¹. Early identification of injury would facilitate prevention and treatment. The gold standard surveillance biopsy has limitations including delayed discovery of injury^{2,3}. No noninvasive test identifies graft injury before it is clinically apparent^{4,5,6}. This project's goal is to develop a novel early marker of subclinical graft injury to facilitate prompt recognition and treatment. Kidney damage activates the renin-angiotensin system (RAS), and the ACE2/Ang-(1-7)/mas pathway counteracts this damage.⁷ The balance, or ratio, between levels of RAS and the ACE2 pathway may be clinically important because the ACE2 pathway counteracts RAS-mediated injury. An increase in ACE and Ang II expression and a decrease in ACE2 and Ang-(1-7) expression on tubular cells may promote renal injury. Tubular damage may increase urinary loss of protective ACE2 and Ang-(1-7), propagating renal damage by allowing ACE and Ang II to stimulate inflammation and fibrosis unopposed.

Aim 1: Diagnose early subclinical graft injury in renal transplant patients with the ratios from ACE2 to ACE and from Ang-(1-7) to Ang II in urine. Hypothesis 1: A shift in the urinary ACE2 to ACE and Ang-(1-7) to Ang II ratios towards ACE2 and Ang-(1-7) predicts early subclinical graft injury diagnosed on renal biopsy. Aim 2: Diagnose chronic subclinical graft injury using the ratios of ACE2 to ACE and Ang-(1-7) to Ang II in the urine.

Hypothesis 2: A shift in the ACE2 to ACE and Ang-(1-7) to Ang II ratios in the urine towards ACE2 and Ang-(1-7) predicts chronic subclinical graft injury on renal biopsy.

Background/Significance

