Angiotensin-converting enzyme (ACE) cleaves angiotensin (Ang) I into Ang II, which operates through the Ang II type 1 receptor (AT₁). The ACE2/Ang-(1-7)/mas pathway is an alternative, less characterized pathway that operates through the mas receptor⁸. ACE2 cleaves Ang II into Ang-(1-7) (figure 1). The exact mechanism of action of Ang-(1-7) is unknown but most data support its anti-inflammatory, anti-fibrotic and immune modulatory effects⁹⁻¹⁷. ACE2, Ang-(1-7) and mas expression is reciprocal to ACE, Ang II and AT₁ expression^{10, 12}. In the kidney, expression of ACE2 and Ang-(1-7) is greatest in the proximal tubules, especially the brush border membrane^{7,10,12,18,19}. The balance between the ACE and ACE2 pathways is critical in preventing renal fibrosis^{7,10,12}. Ang-(1-7) directly blocks Ang II and Ang II's downstream effects through the AT₁ receptor^{10,14,18-27}. ACE inhibitors (ACEi) and AT₁ blockers (ARB) reduce proteinuria and graft injury and improve graft function, independent of blood pressure^{32,37,38}. The ACE2 pathway may be responsible for these effects because it is enhanced at the expense of the RAS^{32,37-42}.

Tubulointerstitial damage decreases ACE2 expression, enhancing ACE and propagating injury^{43,44}. Urine ACE2 protein is elevated in renal transplant patients, independent of serum levels^{45,46}. These findings suggest that tubular damage causes shedding of ACE2 and Ang-(1-7) from the apical membrane of tubular epithelial cells into the tubular lumen and urine. Urinary excretion of ACE2 and Ang-(1-7) is altered in relation to ACE and Ang II. The ratios of ACE2/ACE and Ang-(1-7)/Ang II in urine could be noninvasive markers of subclinical graft injury. It is important to evaluate the balance between the ACE and ACE2 pathways because increased ACE2 could be due to increased expression of ACE2 or decreased ACE. ACE2/Ang-(1-7)/mas directly alters renal inflammation, making it an intriguing biomarker and therapeutic target.

Approach/Methods

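### Aim 2's only adjusted model is a Cox regression for an undefined fibrosis event; the continuous fibrosis measure V_IntFib has no adjusted analysis of its own

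*Combined protocol and SAP*

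**What the plan says.** The Abstract defines the second outcome as "chronic graft injury using Cortical Fractional Interstitial Fibrosis Volume". Approach/Methods explains that stored biopsy tissue is stained with Sirius Red to give a fibrosis measure "that was quantified by computerized image analysis". That is a quantity on a continuous scale.

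Fibrosis can be seen only when a biopsy is taken: "Subjects underwent a six-month surveillance protocol biopsy and some received three-month surveillance protocol or indication biopsies per standard of care".

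Under the Aim 2 primary outcome, the adjusted analysis is this: "Cox regression will be utilized to estimate hazard ratios for the association of biomarker levels with the outcome biopsy-proven graft fibrosis". Time runs from transplant to six months. Right-censoring applies to graft loss, loss to follow-up and withdrawal. Models with time-dependent serum creatinine and eGFR are the comparators.

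Approach/Methods also plans Spearman correlations of the four biomarkers with continuous covariates and outcomes, and ROC summaries. The Power section gives a Pearson correlation of 0.56 at two-sided 0.025, with 30 subjects planned and 29 enrolled. It does not say which two variables are correlated, and it states no target power.

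**The concern.** Three things do not fit together.

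- **The event is not defined.** No section says whether fibrosis counts as biopsy-proven because V_IntFib exceeds a cut-off or because a pathologist reports it. No cut-off is given, and neither is the date that serves as the event time. If the event is a pathologist's reading, V_IntFib has no adjusted analysis at all.
- **The time axis carries little information.** Onset of fibrosis is not observed, only its presence at a biopsy. Most event times would be the date of the six-month biopsy, so the hazard ratio largely reflects the biopsy schedule.
- **The continuous information is used only without adjustment.** Spearman keeps the scale of V_IntFib, but it does not adjust for confounders and does not compare the biomarker with creatinine or eGFR.

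At stake is whether 29 children can give a reproducible adjusted answer to Aim 2, and how much power is lost in getting it.

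**Working it through.** **1. The plan's own figure.** For a correlation, Fisher's z gives power = Φ(atanh(r)·√(n − 3) − z), with z = 2.241 for two-sided 0.025 and atanh(0.56) = 0.6328.

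- n = 30: 0.6328 × √27 − 2.241 gives 85.2%.
- n = 29: 0.6328 × √26 − 2.241 gives 83.8%.
- Solving for 85% power: ((2.241 + 1.036)/0.6328)² + 3 = 29.8.

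The planned 30 is consistent with an unstated 85% target for a correlation. It does not correspond to a Cox calculation.

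**2. Does censoring have work to do?** Final enrollment is 29 (Power), and Approach/Methods says "29 subjects completed the study". Taken literally, nobody was lost or withdrew.

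**3. Adjusted linear regression.** Assume that r = 0.56 applies to biomarker and V_IntFib, that the relation is graded, and that there are k = 3 covariates. Power is then Φ(atanh(r_p)·√(29 − 3 − 3) − 2.241), where r_p is the partial correlation.

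If the covariates explain a share R² of the biomarker and do not act on V_IntFib directly, r_p = 0.56·√(1 − R²) / √(0.56²(1 − R²) + 1 − 0.56²).

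| R² | r_p | Fisher z power | Simulated power |
|---|---|---|---|
| 0 | 0.560 | 79% | 80% |
| 0.20 | 0.517 | 69% | 70% |
| 0.30 | 0.492 | 63% | 65% |

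**4. Adjusted Cox under the same assumptions.** In addition, the event is V_IntFib above a cut-off, all events fall at six months, ties are handled by Efron's method, and the test is the likelihood-ratio test. The document gives no fibrosis rate, so prevalence is assumed. The covariates are independent of the biomarker.

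| Assumed prevalence | Expected events (of 29) | Cox power | Linear power |
|---|---|---|---|
| 10% | 2.9 | about 35% | about 80% |
| 25% | 7.2 | about 50% | about 80% |
| 50% | 14.5 | about 53% | about 80% |

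With covariates explaining 20–30% of the biomarker, Cox falls to roughly 35–43% at 25% and 50% prevalence, against 65–70% for linear.

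At 10% prevalence the adjusted Cox is unreliable. With covariates explaining 20% of the biomarker, simulated false positives were 6.6% against a nominal 2.5%, and coefficients diverged in 26% of data sets.

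**5. Dependence on the cut-off.** When the same simulated children are analysed with cut-offs giving 25% and 50% prevalence, the two Cox tests disagree on significance in about one third of data sets.

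**6. A relation that is not graded.** Let the biomarker shift only once V_IntFib passes a threshold, with Pearson r still 0.56 and three independent covariates.

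| Cut-off relative to the true threshold | Cox power | Linear power |
|---|---|---|
| At or near it | about 84–99% | 82–85% |
| Further off (25% against 50% prevalence, either way) | 48–52% | 82–86% |

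**The case against.** The strongest objection is that a continuous model must win when the relation is simulated as graded, and the plan gives no dose–response shape. Background/Significance describes tubular damage causing shedding into urine, which a threshold could fit as well. This stands. A reader might infer that a continuous model is always the more powerful, but step 6 shows that it is not.

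A reader might also infer that the study was sized on the biomarker–V_IntFib association. The Power section does not say so. It names no variables and also bases enrollment on a 10% incidence of kidney injury. Using r = 0.56 here is an assumption, and so is treating the event as dichotomised V_IntFib.

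It can be said that V_IntFib is already analysed continuously by Spearman. That is true, so the outcome is not ignored; what is missing is adjustment and the comparison with creatinine and eGFR.

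It can also be said that Cox uses the repeated urine samples, taken "daily for 1 week, weekly for 1 month and monthly until 6 months post-transplant". If all events fall at six months, a time-updated Cox model uses only the value current then.

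The added model has limits of its own. The Background says of ACE inhibitors and AT₁ blockers that "The ACE2 pathway may be responsible for these effects because it is enhanced at the expense of the RAS", so ACEi/ARB use is likely to be correlated with the biomarker, and some loss of adjusted power should be expected.

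Finally, the subjects had already completed the study, so replacing the main model now would carry a risk of selective choice. This supports adding an analysis beside the Cox model and not substituting for it.

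**Conclusion.** The concern holds in a conditional form. It is well supported that the adjusted Aim 2 result depends on an event whose definition, cut-off and timing this document does not state; a cut-off may exist in a cited source, but the plan does not adopt one. Confidence in that is high.

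The gain from an adjusted continuous model is about 27 to 45 points (80% against 53% and 35%). It rests on a graded relation, r = 0.56 for biomarker and V_IntFib, dichotomised V_IntFib, assumed prevalences, all events at six months, and covariates independent of the biomarker. It disappears or reverses if a threshold relation holds and the cut-off is at or near the threshold. Confidence in the size of the gain is moderate. None of this shows that the planned Cox model is invalid in general; the unreliability found concerns the adjusted fit with about three events.

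**What to change.** **Add one adjusted analysis.** Regress V_IntFib from the six-month protocol biopsy on each log urinary ratio named in Hypothesis 2. Log-transform V_IntFib if the planned quantile plots call for it, or use ranks. Take the ratio from one stated pre-biopsy sample. Adjust for a few confounders named in advance from the Approach/Methods list. Make the creatinine and eGFR comparison in the same model, using the last pre-biopsy values.

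**Complete the Cox specification and report both.** State what counts as the fibrosis event, the cut-off and its source, and how event time is coded. Present the Cox result beside the new model.

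**Missing urine ratios.** If these are to be imputed, say so explicitly. The Missing Data section plans imputation for covariate values and refers to the biomarkers as predictors, so it does not clearly cover them.

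**Record the timing.** Date the change, label it as made after data collection, and say whether outcomes had been seen.

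**Cost.** No new data are needed. The addition comes after collection and must be read that way. The model yields no hazard ratio and does not use the repeated samples. Any child without a six-month biopsy does not contribute to it. Its power falls below 80% to the extent that the confounders are correlated with the biomarker.
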